5.1 Safety Criteria for Dose Adjustment or Stopping Doses

The principal investigator or sub-investigator will follow the protocol to identify and intervene with subjects experiencing clinical deterioration during study participation. Criteria to determine when a subject requires a higher level of care and discontinuation from the trial intervention are detailed below.

5.2 Investigational Produce Dose Reduction

The daily dosage of investigational product may be reduced by the study physician for any AE determined, by the study physician, to compromise the subject's ability to maintain activities of daily living or if the subject reports undue discomfort. While at the target dose (80 mg/day), the dose may be reduced to 40 mg once daily. If the AE resolves at the lower dose, another attempt to increase the dose to the target dose is appropriate at the study physician's discretion.

5.3 Investigational Product Discontinuation

Subjects who are discontinued from investigational product should continue in the study and complete all assessments, including the follow-up assessments, as well as *Path 180*. If the subject discontinues the investigational product before Study Week 5 then they will not complete the H-LAB paradigm.

- a. **Pregnancy.** Females who become pregnant during the medication phase of the study, Study Weeks 1 through 6, will be immediately discontinued from the investigational product. The investigator must report a pregnancy within 1 working day of the site being aware to the medical monitor.
- b. **Physical Illness.** Subjects will need to be removed from investigational products if they have a serious illness or a disabling condition that precludes them from taking the investigational product.

c. **Adverse Events.** If the subject experiences any AEs that are considered study drug related and for which the investigator has determined that continuation of the study drug could be detrimental to the health of the subject, then drug will be reduced for 1 week, then discontinued, or immediately discontinued as described above.

5.4 Subject Withdrawal or Discontinuation Procedures

Each subject has the right to withdraw consent/assent and withdraw from the study at any time. Parents of minors younger than 18 years of age have the right to withdraw their permission for their child to participate in the study at any time. In addition, the investigator may find it necessary to discontinue a subject for any reason, including (but not limited to) the occurrence of an AE or noncompliance with the protocol.

If a subject withdraws or is discontinued from the study, the reason(s) for the discontinuation from the study will be recorded and a pregnancy test (females only), vital signs, clinical chemistry, C-SSRS, TLFB and an assessment of AEs will be performed as soon as possible after discontinuation from the study.

5.5 Situations Requiring Discontinuation from the Study or Investigational Product

It is possible that there will be some subjects who cannot be safely managed in the clinical study even though investigational products have been discontinued. Examples are given below.

- 1. **Increased Drinking.** Subjects whose alcohol problems worsen and, in the opinion of the principal investigator, sub-investigators, or study nurses or physicians, require a more intense level of care than provided in the study may have the investigational product suspended and referred to more appropriate care.
- 2. Psychiatric Crises. Examples of psychiatric crises include but are not limited to the following:
 - a. Acute psychosis (hallucinations, impaired reality testing, paranoid ideation, etc.) requiring medication and/or hospitalization or intensive outpatient intervention;
 - b. Suicidal or homicidal ideation that results in a credible threat of violence directed at oneself or others:
 - c. Hospitalization for psychiatric symptoms.

Subjects requiring more intensive treatment resulting from acute psychosis or suicidal/homicidal behavior will be referred to local treatment centers, emergency departments, or hospitals as appropriate, but will not be provided with medication or psychotherapy by study staff.

Study Termination Criteria

The principal investigator may terminate the study for reasonable cause after providing written notice to the funding agency in advance of the intended termination. Advance notice is not required if the study is stopped due to safety concerns. If the DSMB terminates the study for safety reasons, the principal investigator will immediately notify the medical monitor, IRB, and funding agency.

Study Endpoints

6.1 Feasibility and Acceptability Endpoints

6.1.1 Primary Feasibility Endpoint

The number and percentage of subjects who completed the 6-week active medication phase will determine feasibility.

6.1.2 Primary Acceptability Endpoint

The Client Satisfaction Questionnaire (CSQ-8), which ranges in scores from 8 to 32 (higher scores indicate higher satisfaction), will determine acceptability. Treatment satisfaction will be considered acceptable if the number and percentage of subjects who rate their treatment experience in the "satisfactory" or "highly satisfactory" range on the CSQ-8 is $\geq 80\%$.

6.2 Secondary Outcome: Alcohol Craving Assessed in the H-LAB Paradigm

The secondary endpoint will be alcohol craving assessed during a laboratory alcohol-cue exposure paradigm, at week 5. During the paradigm, participants rated their alcohol craving immediately following exposure to water cues and again immediately following exposure to alcohol cues.

The primary measure of alcohol craving will be the number and percentage of participants who report any level of alcohol craving during a laboratory alcohol-cue exposure paradigm using the following single item: *How strong is your craving to drink alcohol?* Scores range from 0 (None) to 20 (Extremely Strong). Individuals who endorse any level of alcohol craving (e.g., > 1) are considered to experience craving. Individuals who do not report any alcohol craving (e.g., 0) will be regarded as non-craving.

Safety Monitoring Plan

Safety monitoring will be conducted throughout the study; therefore, safety concerns will be identified by continuous review of the data by the principal investigator, clinic staff, medical monitor, and study nurses and physicians.

The Brown University IRB, medical monitor, principal and sub-investigators, and study nurses and physicians will review any safety concerns throughout the trial. In addition, a DSMB will participate in this study.

Quality control is central to all aspects of the activities detailed in this proposal to ensure clinical data accuracy and integrity. Day-to-day oversight of data quality will be delegated to the principal investigator, [name] and/or his designee. With assistance from our core team, he will provide direction with the development of data collection forms, recruitment and tracking databases, data management tasks, and statistical analyses and interpretation. The principal investigator or his designee will oversee the production of standard labels/codebooks for all data collection activities. He or his designee will oversee the production of reports that will track indices of project success, which will be reviewed weekly or biweekly at meetings of our core team, where issues or concerns will be deliberated and corrective action plans put into place.

Our research team has substantial experience in the design and implementation of data management procedures that: (a) ensure the validity and integrity of data; (b) guarantee the accuracy and completeness of data during data collection, transmission, and analysis; and (c) maintain confidentiality and data security. These procedures are in accordance with FDA and ICH standards. All procedures involving human research subjects will be performed at the Brown CAAS. The principal investigator will be responsible for coordinating activities of the data safety and monitoring, including arranging weekly meetings and communications, and identifying and reviewing subject materials.

Medical Monitor: A medical monitor, [name], MD, PhD, has been appointed by the principal investigator. [name] will be available for making recommendations to the investigator on the severity of any SAEs and the relatedness to the study interventions. [name] will also be responsible for tracking and assessing trends in the AEs reported.

Data and Safety Monitoring Board: Although an independent DSMB is not required because this project is not a Phase III clinical trial, we will assemble a DSMB. The DSMB for this project will consist of senior researchers in the field who have expertise in adolescent or pharmacotherapy research or both, and will include at least one physician.

No member of this DSMB will be directly involved with the conduct of this study or have a conflict of interest with this study. The DSMB will meet at the onset of the study, at least once quarterly thereafter, and when 25%, 55%, and 85% of subjects have been enrolled. Ad hoc meetings may also be scheduled if the need arises (e.g., in the event of a study-related SAE). The DSMB will discuss study conduct and progress, subject safety, and, when appropriate, efficacy. Specifically, items to be reviewed include: interim/cumulative data for evidence of study-related adverse events, interim/cumulative data for evidence of efficacy when 85% of subjects have completed the protocol (if necessary), data quality, completeness and timeliness; adequacy of compliance with goals for recruitment and retention, including those related to females and minorities; adherence to the protocol; and factors external to the study, such as scientific or therapeutic developments that may impact subject safety or the ethics of the study.

The Board will be blinded to subjects' actual randomized group assignments but may request at any time that the blind be broken, if concerns arise from the blinded data. Ad hoc meetings will be convened if SAEs occur that are considered at least possibly related to the investigational product. At the end of each meeting, the DSMB will make a recommendation regarding trial continuation and will forward that recommendation to the principal investigator who will forward it to the Brown University IRB and the Program Official at the funding agency (i.e., NIAAA).

In addition, the investigative team will meet on a weekly or biweekly basis to evaluate the study's recruitment and retention procedures, to monitor any potential significant benefits or risks that may occur to warrant the early termination of the study and to monitor study progress.

Adverse Event Assessment

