2.1 Primary Objectives

- Evaluate the feasibility, acceptability, and tolerability of atomoxetine (40 mg/day for 3 days then 80 mg/day thereafter) plus MET-CBT (i.e., "Path 180") for 6 weeks among adolescents with AUD as confirmed by the Diagnostic and Statistical Manual of Mental Disorders Fifth Edition (DSM-5TM).
- Apply our H-LAB paradigm to evaluate the effects of atomoxetine on intermediate phenotypes associated with alcohol use and outcomes in clinical trials. We hypothesize that atomoxetine, as compared to placebo, will reduce the likelihood of craving in the human laboratory during *in vivo* alcohol cue reactivity.

Study Interventions

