The H-LAB paradigm will follow our standardized procedures. Audio-recorded instructions ensure standardization within and across subjects. After attaching the physiological monitor (i.e., blood pressure cuff), the session begins with a 3-minute relaxation period that involves subjects sitting quietly and doing nothing. Then a 3-minute water trial begins, in which subjects hold and smell a glass of water as a standard procedure to control for the effects of simple exposure to any potable liquid, including all aspects of stimuli and movement except the nature of the beverage. A second 3-minute relaxation period follows the water trial. Next, subjects hold and smell a glass of their most desired or commonly consumed alcoholic beverage for two consecutive 3-minute alcohol trials. Order of water and alcohol trials is not counterbalanced due to known carryover effects. The water is accompanied by a commercially labeled water bottle and alcohol by the bottle or can from which it was poured and prepared as the teen usually drinks it. Across water and alcohol trials, subjects sniff the beverage for 5 seconds each time a tone sounds: 13 tones sound at variable intervals during each 3-minute block to ensure that all youth receive the same olfactory exposure. Observation via one way window ensures compliance. Subjects rate their alcohol craving after each 3-minute trial.

After every 3 minutes of exposure, each subject will rate his/her urge to drink alcohol using a visual analogue scale (VAS). The primary efficacy endpoint in the H-LAB is the "strength" of alcohol craving measured on a visual analogue scale (VAS; Item 1 below).

Following the H-LAB paradigm, subjects will receive a 7-day supply of the blinded study medication, and the dosing schedule will be reviewed. The subject will be instructed to bring the blister cards with them to the next visit so the project staff can perform drug accountability (capsule counts). The subject will also be instructed to contact project staff if they are experiencing any intolerable adverse events.

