8.2 Secondary Outcome: Alcohol Craving Assessed in the H-LAB Paradigm

The secondary endpoint will be alcohol craving assessed during a laboratory alcohol-cue exposure paradigm, at study week 5. During the paradigm, participants rated their alcohol craving immediately following exposure to water cues and again immediately following exposure to alcohol cues. The primary outcome measure will be is the number and percentage of participants who report any level of alcohol craving during a laboratory alcohol-cue exposure paradigm (following exposure to alcohol cues) using the following single item: *How strong is your craving to drink alcohol?* Scores range from 0 (None) to 20 (Extremely Strong). Individuals who endorse any level of alcohol craving (e.g., > 1) are considered to

experience craving. Individuals who do not report any alcohol craving (e.g., 0) will be regarded as non-craving. Using generalized estimating equations, we compared the likelihood of alcohol craving as a function of medication condition.

Quality Control and Quality Assurance

This study will be conducted under International Conference on Harmonization (ICH) Good Clinical Practice (GCP) guidelines and all applicable regulatory requirements.

Actions to ensure the accuracy and reliability of data include the selection of qualified investigators and appropriate study centers; the review of protocol procedures with the investigator and study personnel prior to study start; the design of suitable source documents with appropriate instructions for use; the internal audit of source data according to GCP and internal procedures to ensure their accuracy, completeness, and verifiability; as well as the periodic site monitoring by the Sponsor's representatives (clinical monitors). The Project Coordinator or Project Director will review source documents and CRFs for accuracy and completeness. Any discrepancies will be resolved with the investigator, as appropriate.

Audits and Inspections

Authorized representatives of the Sponsor and the IRB may visit the site to perform audits or inspections, including source data verification. The purpose of the audit or inspection is to systematically and independently examine all study related activities and documents to determine whether these activities were conducted, and data were recorded, analyzed, and accurately reported according to the protocol, GCP guidelines, and any applicable regulatory requirements.

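### The craving outcome is worded as any level above none, but its printed cut is > 1, so a score of 1 on the 0–20 item falls in neither category

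*Combined protocol and SAP*

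**What the plan says.** The item asks how strong the subject's craving to drink alcohol is, and its lowest anchor, 0, means none. Section 6.2 names the measure as "the number and percentage of participants who report any level of alcohol craving" during alcohol-cue exposure. It then sets two categories:

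- The craving category carries the number > 1: "Individuals who endorse any level of alcohol craving (e.g., > 1) are considered to experience craving".
- The other category carries the number 0: "Individuals who do not report any alcohol craving (e.g., 0) will be regarded as non-craving".

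Section 8.2 repeats the item, the range and both categories with the same numbers. It then says of the analysis, by generalized estimating equations, that "we compared the likelihood of alcohol craving as a function of medication condition". Section 2.1 states the matching hypothesis for the second primary objective: atomoxetine "will reduce the likelihood of craving in the human laboratory". Section 4.7 describes the rating as a visual analogue scale. No section gives the scoring step of that scale.

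**The concern.** A binary endpoint needs a rule that places every possible score in exactly one class. The words do this: on a scale whose zero means none, any level of craving is any score above zero. The printed numbers do not, because craving starts above 1 and non-craving is 0, with a gap between them.

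A programmer working from the number has two options for a score of 1: count it as non-craving (everything not above 1), or leave it out because neither rule covers it. Both differ from the outcome that the words describe. The lowest positive scores are also the ones that an any-versus-none endpoint exists to separate from zero.

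The number cannot simply be dismissed as a misprint. Section 1.2 notes that some cue-reactivity researchers count any change as a response, while others require a minimum such as an increase of more than one point. That passage concerns change scores and not this item, but it shows that a reader could take > 1 as a deliberate threshold.

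What is at stake is the only between-arm efficacy outcome with an analysis in section 8, and with it the hypothesis of the second primary objective.

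**Working it through.** **Classification of scores.** The inputs are the 0–20 range and the two printed categories, from 6.2 and again 8.2.

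| Rule for craving (non-craving = 0) | Craving, whole-number scores | Unclassified, whole numbers | Unclassified, 0.1 steps (assumed) |
|---|---|---|---|
| > 1 (printed) | 2–20 (19 values) | 1 | 0.1–1.0 (10 values) |
| ≥ 1 | 1–20 (20 values) | none | 0.1–0.9 (9 values) |
| > 0 (the words) | 1–20 (20 values) | none | none |

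The 0.1 step is an assumption, since the documents do not say how the visual analogue scale is scored. Only > 0 leaves no gap under either scoring.

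**Weight of one subject.** The target is 21 completers per group, with 50 randomized at about 1:1 (section 1.4).

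- 1/21 = 4.8 percentage points; 1/25 = 4.0 points.
- Three subjects in a 21-subject arm: 3/21 = 14.3 points.

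**Illustration.** The counts below are assumed, not taken from the documents. There are 21 per arm, and exactly three subjects score 1. The difference is placebo minus atomoxetine in percent craving.

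*Three scores of 1 on atomoxetine* (atomoxetine: 12 above 1, 3 at 1, 6 at 0; placebo: 18 above 1, 3 at 0):

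| Coding of a score of 1 | Atomoxetine | Placebo | Difference (points) | Fisher p |
|---|---|---|---|---|
| Non-craving (> 1) | 12/21 = 57.1% | 18/21 = 85.7% | 28.6 | 0.085 |
| Craving (> 0) | 15/21 = 71.4% | 18/21 = 85.7% | 14.3 | 0.454 |
| Dropped | 12/18 = 66.7% | 18/21 = 85.7% | 19.0 | 0.255 |

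*Three scores of 1 on placebo* (atomoxetine: 12 above 1, 9 at 0; placebo: 15 above 1, 3 at 1, 3 at 0):

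| Coding of a score of 1 | Atomoxetine | Placebo | Difference (points) | Fisher p |
|---|---|---|---|---|
| Non-craving (> 1) | 12/21 = 57.1% | 15/21 = 71.4% | 14.3 | 0.520 |
| Craving (> 0) | 12/21 = 57.1% | 18/21 = 85.7% | 28.6 | 0.085 |
| Dropped | 12/21 = 57.1% | 15/18 = 83.3% | 26.2 | 0.096 |

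**Milder splits.** Moving from > 1 to > 0 adds (number of 1s)/21 to each arm, so the difference changes by the net imbalance divided by 21.

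- Equal numbers of 1s in both arms: no change.
- Two in one arm and one in the other: 1/21 = 4.8 points.
- Three in one arm and none in the other: 14.3 points, as tabulated.

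If three 1s fell at random among 42 subjects, all three would land in the same arm with probability 2 × C(21,3)/C(42,3) = 2 × 1330/11480 = 0.23.

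The p-values come from simple 2×2 tests; the planned generalized estimating equations may give others. The documents state no alpha, and every Fisher p here exceeds 0.08, so nothing is claimed about significance.

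**The case against.** The strongest reply is that the definition has no gap. Its words are exhaustive and mutually exclusive, the outcome sentence itself carries no number, and both numbers are introduced as examples. A score above 1 is an example of some craving, and 0 is an example of none. On that reading a 1 is craving and the matter is editorial. This is right about intent. It does not help an analyst who codes from the only numeric cut printed, which appears twice, including in the statistical methods.

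A second reply is that the source may have read ≥ 1 and lost a mark in text extraction. That cannot be ruled out, but the ≥ sign survives elsewhere (4.3.1, 6.1.2) and > 1 appears identically in both sections. If scores are recorded in fractions, ≥ 1 would still leave a gap.

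Third, the wider gap between 0 and 1 exists only with fractional scoring, which the documents do not state. On whole numbers, one value of 21 is affected. That stands.

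Fourth, the illustrations place all three scores of 1 in one arm, which is the extreme case. That also stands: an even split leaves the difference unchanged, and a two-to-one split moves it by 4.8 points. The firm figure is 4.8 points per net affected subject; halving or doubling is what can happen, not what is expected.

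Finally, sections 6.2 and 8.2 label this a secondary outcome in a proof-of-concept study. Section 2.1 nevertheless lists its hypothesis under the primary objectives.

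**Conclusion.** The concern holds. In both 6.2 and 8.2 the printed cut contradicts the words it is meant to illustrate, and a score of 1 has no numeric class anywhere in the document. The conflict in the text is certain. Its effect on the result is not known: it depends on how many subjects scored 1 (or between 0 and 1), in which arm, and how the data were coded, and the documents give none of this. The number affected may be zero, and the direction of any shift cannot be stated.

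This should be fixed: it is a wrong threshold in an outcome rule, it could matter in arms of about 21, and the correction follows the plan's own words.

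**What to change.** In 6.2 and 8.2, replace the parenthetical cut for craving with *score > 0* and the one for non-craving with *score = 0*, and drop the wording that makes them examples. Use > 0 in preference to ≥ 1, because it holds whether or not fractions are recorded.

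The past tense in 8.2 suggests that the analysis may already have been run. If so, the sponsor should confirm which coding was used, including whether any scores of 1 were dropped, and rerun the craving table if it was > 1.

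The cost is a few characters in two sections and at most one table. There is no cost to patients or to data collection.

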7.1 Adverse Events and Serious Adverse Events

The investigator and study project staff are responsible for the detection, documentation, classification, reporting, and follow up of events meeting the definition of an adverse event (AE) or serious adverse event (SAE).

